##### **SECONDARY OBJECTIVES:**

- To evaluate microvessel density (MVD) and p53, MDM2, PTEN and VEGF/PDGF pathways by IHQ expression and their correlation with prognosis as well as their role as predictive factors to treatment with Pazopanib (Response, PFS and OS).
- To evaluate serum levels of several angiogenic factors/cytoquines using Luminex XMAP Technology at baseline, after the first 3 weeks of treatment, at maximum response and at progression and their predictive value for survival and response to treatment: VEGF-A, PIGF-1, SDF-1 alpha (CXCL12), TNF alpha, IL-8, IL-6, PDGF –beta, HGF, E- Selectine, ICAM1, MMP-9 and FGFb.
- To analyse PIK3CA mutations in order to demonstrate if those liposarcomas with PIK3CA mutations defines a subgroup of patients with differential response to Pazopanib.

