### STUDY OF BIOMARKERS:

Paraffin-embedded samples from 74 original tumors and if clinically acceptable (ex. superficial or easily accessible locations), tumour biopsy at study entry will be collected and the following analysis will be carried out:

- Microvessel density on full sections of the tissue.
- Immunohistochemical profile of angiogenic markers and p53, MDM2 and PTEN.
- Quantitative RT-PCR of a panel of angiogenic markers.

Serum from peripheral blood will be performed (4 per subject):

1. Within 72 hours prior starting the treatment (basal).
2. Within 72 hours after the first 3 weeks of treatment.
3. Within 72 hours after radiological response is documented.
4. Within 72 hours after progressive disease is documented.

Methodology:

a) Microvessel density and immunohistochemistry: Full sections of paraffin-embedded material will be stained with anti-CD34 or anti-CD31 and evaluated using a light microscope and specific software for measuring microvessels with no muscular walls.

Tissue microarrays (TMA) will be constructed containing at least two cores (1.0 mm in diameter) from each tissue sample.

At least the following antibodies will be tested: VEGF, PDGF, VEGFR-1 (flt-1), VEGFR-2 (flk-1/KDR), PDGFR-alfa, PDGFR-beta, HIF-1, TSP-1, VE-cadherin, p53, MDM2 and PTEN.

Additional tests could be considered depending of new findings or evidences in the field of tumor angiogenesis.

b) RT-PCR Low density arrays for the expression of angiogenic factors: We will perform an RNA extraction from paraffin embedded material and an RT-PCR low density expression array containing 94 angiogenesis-related genes will be analysed. These arrays include known angiogenesis growth factors like VEGF, and known matrix derived inhibitors such as endostatin. Additionally, the panel contains markers and targets for angiogenesis and lymphangiogenesis.

List of genes included:

- Angiogenic growth factors (28): ANG, ANGPT1, ANGPT2, ANGPT4, CSF3, CTGF, CXCL12, ECGF1, EDIL3, EPHB2, FGF1, FGF2, FGF4, FST, GRN, HGF, IL8, LEP, MDK, PDGFB, PROK1, PTN, TGFA, TGFB1, TNF, VEGF, VEGFB, VEGFC.
- Angiogenesis inhibitors (37): ADAMTS1, ANGPTL1, BAI1, CHGA, COL15A1, COL18A1, COL4A1, COL4A2, COL4A3, CXCL10, CXCL2, F2, FBLN5, FGA, FLT1, FN1, HSPG2, IFNB1, IFNG, IL12A, ITGA4, LECT1, PF4, PLG, PRL, SEMA3F, SERPINB5, SERPINC1, SERPINF1, THBS1, THBS2, TIMP2, TIMP3, TNFSF15, TNMD, TNNI1, VASH1.

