- Angiogenesis markers (10): AMOT, ANGPTL2, ANGPTL3, ANGPTL4, CEACAM1, HEY1, ITGAV, PECAM1, PGK1, XLKD1.
- Angiogenesis targets (13): EDG1, ENPP2, FLT3, FLT4, ITGB3, KDR, KIT, NRP1, NRP2, PDGFRA, PDGFRB, TEK, TIE1
- Lymphangiogenesis markers (5): CD44, CDH5, FIGF, FOXC2, PROX1
- Controls (2): 18S, GAPDH

c) Serum cytokine markers: The Luminex technology will be employed for the analysis of 12 cytokines [VEGF-A, PlGF-1, SDF-1 alpha (CXCL12), TNF alpha, IL-8, IL-6, PDGF-beta, HGF, E-Selectine, ICAM1, MMP-9 and FGFb].

d) Analysis of PIK3CA mutations: DNA extraction, amplification of exons 4, 7, 9 and 20 of PIK3CA by PCR and direct sequencing will be performed.

[figure not shown]
The proposed biomarker study includes analysis of tumor tissue at diagnosis and serum cytokines and growth factors at different phases within the treatment schedule. In the case of serum, the kinetic profile of each biomarker will be considered (decreased, constant, increased). All analysed parameters will be correlated with: Progression-free survival (PFS) assessed 12 weeks after start of treatment (According the RECIST criteria 1.1); median PFS; objective tumor response; overall survival and histopathological parameters. For the statistical analysis, we will use binary variables reflecting the positivity status of the measures (yes or no; presence/absence). Association with histopathological parameters, and objective tumor response, all categorical, will be also assessed using a chi-square test to determine homogeneity or linear trend for ordinal variables. The significance level will be set at 5%. To study the impact of the histological, immunohistochemical and molecular factors on progression-free survival (PFS) and overall survival (OS), the Kaplan-Meier proportional risk test (log rank) will be used. Evidence of the relative risk for each patient will be also provided by means of a Cox proportional hazards model using stepwise selection to identify the independent predictors of poor outcome.

We do not plan to use multivariate analysis to analyse biomarkers. Standard pre-post univariate tests will be used instead.

For the kinetic profile of the serum biomarkers, each variable will be considered as continuous. A correlation between the growth factor or cytokine levels with the different points of the treatment schedule will be considered and the slope value will be used in

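### Section 13 plans about 476 marker-by-outcome tests at an unadjusted 5% level; if no marker matters, about 24 false-positive associations are expected, falling on roughly 6 to 22 markers

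*Protocol*

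**What the plan says.** The statistical paragraph of Protocol Section 13 opens the analysis to the whole panel: "All analysed parameters will be correlated with: Progression-free survival (PFS) assessed 12 weeks after start of treatment". It adds further outcomes: "median PFS; objective tumor response; overall survival and histopathological parameters". After a sentence on chi-square tests for histopathology and objective response, it states: "The significance level will be set at 5" per cent. Log-rank tests and a Cox model are then named for PFS and OS, with no level of their own. No test is named for 12-week PFS. The section goes on to say that biomarkers will be analysed univariately.

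The panel is set out in the same section:

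- Gene expression: "an RT-PCR low density expression array containing 94 angiogenesis-related genes will be analysed". The itemised list has 28 growth factors, 37 inhibitors, 10 angiogenesis markers, 13 targets, 5 lymphangiogenesis markers and 2 controls.
- Immunohistochemistry: 12 antibodies, given as a minimum.
- Serum: 12 cytokines, sampled up to four times.
- Microvessel density and PIK3CA mutation status.

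More may follow: "Additional tests could be considered depending of new findings or evidences in the field of tumor angiogenesis". The cut-off for serum slopes is to be set after looking at the whole series.

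The two translational primary objectives (Protocol 4.3.3 and 13, repeated in SAP 1.16.3) name the tumour's angiogenic status and the serum cytokine profile. Each is a whole panel, not a single marker or a marker-outcome pair. The available SAP text shows no analysis for these objectives.

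**The concern.** When many markers are each tested at 5%, some will reach significance by chance, and the number grows with the number of tests. The plan offers nothing to separate those from real associations: no named lead marker, no ordering, no false-discovery control, no validation step, and no statement that the results are exploratory. At most 74 tumours are planned.

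What is at stake is how the translational results are read. They are to be published separately after the main paper (Protocol 12.6.2). A reader who sees a list of markers with p below 0.05, without the number of tests behind it, could take chance findings for predictors of pazopanib benefit.

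**Working it through.** The documents give no number of tests, expected false positives or family-wise error for Section 13, so there is no stated figure to reproduce.

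**1. Markers.** Non-control genes as listed: 28 + 37 + 10 + 13 + 5 = 93. The text says 94, and the list gives 95 with the two controls; the difference is immaterial. Adding the rest: 93 genes + 12 antibodies + 12 cytokines + 1 microvessel density + 1 PIK3CA = 119.

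**2. Tests.** The efficacy outcomes are 12-week PFS, PFS, objective response and OS, which is four. 119 × 4 = 476 tests, counting each cytokine once.

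**3. Expected false-positive tests if no marker matters.** Number of tests × 0.05 = 476 × 0.05 = 23.8. With 94 genes it is 480 × 0.05 = 24.0. For one outcome it is 119 × 0.05 = 5.95. These expectations do not depend on correlation, but they do require each test to have a true 5% size.

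**4. Markers flagged at least once.** One marker can produce several of the 23.8 false positives, so the number of markers is smaller.

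| Assumed correlation between the four outcomes' test statistics | Expected markers flagged |
|---|---|
| 0 (independent): 119 × (1 − 0.95⁴) | 22.1 |
| 0.5 | about 18.5 |
| 0.7 | about 15.5 |
| 0.9 | about 11.1 |
| 1 (fully dependent): 119 × 0.05 | 5.95 |

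The middle rows use equicorrelated normal statistics and two-sided tests. The documents give no correlation. The outcomes do overlap: 12-week PFS (Protocol 10.1.1) is a dichotomised view of PFS (10.1.2).

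**5. Chance of at least one false positive for a single outcome.** If the tests are independent, this is 1 − 0.95^m for m markers. The other columns use equicorrelated normal statistics at assumed marker correlations.

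| Set | Independent | 0.5 | 0.8 |
|---|---|---|---|
| All 119 markers | 99.8% | 81% | 37% |
| 12 baseline cytokines | 46% | 32% | 19% |

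**6. What the count leaves out.** Histopathology, repeated serum samples and slopes, analyses by cohort, data-driven cut-offs and later additions are not in the 476. As one example, counting the 12 cytokines at four time points gives 93 + 12 + 1 + 1 + 48 = 155 variables, and 155 × 4 × 0.05 = 31 expected false positives.

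**The case against.** Several points on the other side are fair.

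- **The 476 is partly an inference.** The 5% sentence follows the chi-square sentence. Applying it to the log-rank and 12-week PFS tests is the natural reading, because no other level is given, but it is not explicit. The log-rank sentence also does not name serum cytokines. This stands as a qualifier. Even one outcome gives about 6 expected false positives.
- **The true size may not be 5%.** With at most 74 patients and possibly few responders, chi-square tests on binary markers can have a true size above or below nominal. This stands, mainly for the response tests.
- **The 5% is a per-test level.** A reader might infer that the plan promises a 5% error rate for each translational objective and breaks that promise. It does not: no family-wise rate is claimed anywhere.
- **The wording is not confirmatory.** A reader might take the PIK3CA objective as promising proof. It reads "in order to demonstrate if those liposarcomas with PIK3CA mutations defines a subgroup of patients with differential response to Pazopanib", which poses a question, and the two translational primary objectives speak only of evaluating. No change of wording is needed there.
- **No trial decision depends on it.** The stage 1 and final rules in Protocol 10.4 use 12-week successes only. This stands and limits the weight of the point.

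It might also be said that biomarker work is understood to be exploratory. The plan does not say so, and it designates primary translational objectives and a significance level. Section 13 also mentions a stepwise Cox model, which conflicts with its statement that no multivariate analysis is planned. That needs reconciling separately; stepwise selection would not control error across the univariate tests.

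**Conclusion.** The gap is real: about 119 markers, four efficacy outcomes, one unadjusted level, and no multiplicity control, hierarchy or exploratory label. If no marker matters and each test has 5% size, about 24 false-positive associations are expected, on roughly 6 to 22 markers.

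Two stronger readings are tempting and are not supported. One is that about 24 markers would be falsely flagged: 23.8 counts marker-outcome tests, and the number of distinct markers is at most about 22, lower when outcomes overlap. The other is that several false markers are almost certain. That fits only weakly correlated markers. At an assumed correlation of 0.8, which is possible in a panel devoted largely to angiogenesis, the chance of even one false positive for a given outcome is 37%.

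The result rests on three assumptions: the 5% level applies to all four outcomes, the tests have about nominal size, and the correlations are as assumed. This is a worthwhile, inexpensive improvement to the translational analysis, and it does not bear on the primary endpoint.

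**What to change.** In the statistical paragraph of Protocol Section 13, with a matching entry in the SAP:

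1. State the level that applies to every translational test, including log-rank and 12-week PFS.
2. Keep raw p-values and add Benjamini-Hochberg false-discovery control, for example at 10%, within two families across the four efficacy outcomes:
   - (a) Tissue markers: genes, immunohistochemistry, microvessel density and PIK3CA. As listed, 93 + 12 + 1 + 1 = 107 markers, and 107 × 4 = 428 tests.
   - (b) Serum cytokines: baseline levels and kinetic slopes. With one slope per cytokine, 12 + 12 = 24 variables, and 24 × 4 = 96 tests.
3. Report q-values and the number of tests in each family.
4. Label all translational results hypothesis-generating, including any tests added later.

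The 10% level and the two-family split are choices the sponsor may vary, provided they are fixed before the data are examined.

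The cost is a few sentences and an extra output column, with no new patients, samples or visits. The downside is that fewer markers will be called significant, and weak true associations may be missed. The Simon design and its decision rules do not change.

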## 4. RATIONALE AND OBJECTIVES

### 4.1 BACKGROUND AND RATIONALE

Soft tissue and bone sarcomas are rare malignant tumors, which encompasses a large family of more than 50 histologically distinct tumor subtypes, all of which share a putative mesenchymal origin. In the case of soft tissue sarcomas (STS) surgical excision is the mainstay of treatment, but despite curative surgery, around half of patients develop distant metastases and die from disease. Few therapeutic approaches are currently available to patients with unresectable, locally advanced, or metastatic STS and only anthracyclines, ifosfamide and trabectedine have shown activity, with response rates of 20–40% in previously untreated patients. Recent and ongoing trials have investigated a variety of combination chemotherapeutic regimens (variously employing ifosfamide, doxorubicin, gemcitabine, temozolamide, vincristine, cisplatin, and dacarbazine, among others) as well as targeted therapies, which in some cases have yielded improvements in response rate but which have had little impact on survival. No other medical option is currently available, and the median survival of patients with soft-tissue sarcoma with non-resectable metastases is around 12-15 months, and approximately 8 months after second line chemotherapy.

Liposarcomas are STS which account for at least 20% of all STS in adults. They can be further classified into 3 histologically and biologically different subtypes: well-differentiated liposarcoma/de-differentiated liposarcoma (ALT-WD), myxoid or round cell liposarcoma and pleomorphic liposarcoma.

ALT-WD liposarcomas are locally aggressive rarely metastasising tumors characterized by ring or giant marker chromosomes on the cytogenetic analysis and by amplification of the 12q13-21 region on FISH (MDM2, CDK4 and HMGIC). They account for about 40% of liposarcomas with a 5 year OS around 80%. In a series of WD/DD treated with several regimens response rate was 12.5% OS 15 months and median PFS 3.6 months(95 CI: 3.3-5.9)

Mixoid /round cell liposarcoma accounts for 45-50% of all liposarcomas. They tend to metastasise to unusual soft tissue and bone locations. High histologic grade with more than 5% of round cell component is associated with a 5-year OS of 50% approx. They are characterized by t(23;16)(q13-14;p11) which leads to the fusion of CHOP and TLS genes.

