### **10.4. Sample Size and Statistical analysis**

The drug will be separately investigated in the following liposarcoma subtypes:

- Well-differentiated liposarcoma/dedifferentiated liposarcoma (ALT-WD)
- Myxoid/round cell liposarcoma.

The Simon two-stage design will be separately applied in each stratum. A total of 17 patients will be included in each stratum for the first step of the trial. For the second step, 20 (up to 37) additional patients will enter in each stratum provided the results of the first step were positive. A total of 37 patients could enter the study in each stratum.

Success will be defined as documented disease stabilization or response after at least 12 weeks of therapy.

The following design characteristics and decision rules apply separately to each stratum. The Simon optimal one sample two stages testing procedure (optimal design) will be used with the following hypotheses:

- Success in 20% of the cases or less in one of the strata will be considered as unacceptable, and would not warrant further investigation (null hypothesis). Therefore, the value of P0 will be taken as 20%.
- Success in 40% of the cases or more in one of the strata will be considered as an acceptable result warranting further investigation of the drug in this histology (alternative hypothesis). Therefore, the value of P1 will be taken as 40%.

These two reference values are based on a retrospective analysis of the EORTC STBSG database of patients treated with 2nd line therapy.

Under those hypotheses, a total of 37 eligible and treated patients will need to be recruited in each stratum and followed for at least 12 weeks. The size of the type I and type II errors is 10% ( $\alpha=\beta=0.1$ ).

A total of 17 eligible and treated patients will be included (in each stratum) in the first step of the study.

1. If  $\leq 3$  successes are observed in a stratum, the trial will be stopped in this stratum with the conclusion that the drug should not be further investigated in this histology.
2. Else, patients will continue to be accrued until 37 eligible patients have been recruited and have started therapy. If 11 or more successes are observed in those 37 patients, we will conclude that the results of this trial warrant further investigation in this histology.

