### SECONDARY OBJECTIVES:

- To evaluate microvessel density (MVD) and p53, MDM2, PTEN and VEGF/PDGF pathways by IHQ expression and their correlation with prognosis as well as their role as predictive factors to treatment with Pazopanib (Response, PFS and OS).
- To evaluate serum levels of several angiogenic factors/cytoquines using Luminex XMAP Technology at baseline, after the first 3 weeks of treatment, at maximum response and at progression and their predictive value for survival and response to treatment: VEGF-A, PIGF-1, SDF-1 alpha (CXCL12), TNF alpha, IL-8, IL-6, PDGF –beta, HGF, E- Selectine, ICAM1, MMP-9 and FGFb.
- To analyse PIK3CA mutations in order to demonstrate if those liposarcomas with PIK3CA mutations defines a subgroup of patients with differential response to Pazopanib.

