order to distinguish those cases with no change, negative or positive trend. The threshold will be calculated after considering the behaviour of the whole series. The slope value will be considered from baseline and using the nonparametric Wilcoxon signed-rank test. However other analysis will be undertaken depending of the behaviour of the measures.

For sending the biological samples, please contact to:

An additional document will be provided in the Investigator Site File with detailed biological sample collection and shipment procedures.

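### Section 13 does not stratify its biomarker tests by cohort, so a marker that follows histology, such as MDM2, could look prognostic if the two cohorts differ in outcome

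*Protocol*

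**What the plan says.** Protocol section 13 has its own analysis paragraph. The tissue material is "Paraffin-embedded samples from 74 original tumors", which equals two cohorts of 37. A secondary objective is "To evaluate microvessel density (MVD) and p53, MDM2, PTEN and VEGF/PDGF pathways by IHQ expression and their correlation with prognosis", and as predictors of benefit from pazopanib. For time-to-event outcomes the text begins "To study the impact of the histological, immunohistochemical and molecular factors on progression-free survival (PFS) and overall survival (OS"), and names a log-rank test and a stepwise Cox model for independent predictors. Chi-square is named for histopathological parameters and objective response, at a 5% level. Twelve-week PFS is among the outcomes to be correlated with markers, but no test is named for it. For the serum slopes, "The threshold will be calculated after considering the behaviour of the whole series". Directly after the Cox model the protocol says that multivariate analysis of biomarkers is not planned and that univariate tests will be used. Nowhere in section 13 is cohort a stratum, an adjustment variable or a subgroup.

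Three other places matter:

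- Section 5.1 ends its account of the 17- and 37-patient rule with a general statement that analysis is by stratum. Section 10.4 estimates PFS and OS by stratum.
- Section 4.1 describes the well-differentiated/dedifferentiated (ALT-WD) group as characterised by ring or giant marker chromosomes and "amplification of the 12q13-21 region on FISH (MDM2, CDK4 and HMGIC"), and the myxoid/round cell group by a CHOP-TLS fusion.
- SAP section 1.16.3 repeats the translational objectives. The SAP text available gives no biomarker analysis.

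**The concern.** Histology confounds a marker-outcome test when two conditions hold: the marker's frequency differs between the cohorts, and so does the outcome. For MDM2 the protocol's own background makes the first condition likely. The second is open: the cohorts have separate two-stage designs, so one may succeed where the other fails. If both conditions hold and the cohorts are analysed together, a marker that does nothing inside either cohort inherits the difference between them. It could then be reported as a prognostic factor, or as a marker of pazopanib activity, when it only restates the diagnosis. The reverse can also happen, with a real within-cohort effect masked.

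The stepwise Cox model might have picked up histology, but nothing forces it in, and the sentence that follows withdraws multivariate analysis. No adjustment is therefore secured.

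**Working it through.** **1. The plan's own figures.** Section 10.4 gives P0 ("Therefore, the value of P0 will be taken as 20"%), P1 ("Therefore, the value of P1 will be taken as 40"%) and the error rates ("The size of the type I and type II errors is 10"% each), with stopping at 3 or fewer of 17 and a positive result at 11 or more of 37. The probability of a positive result is the sum over x = 4 to 17 of b(x; 17, p) × P(Bin(20, p) ≥ 11 − x). It is 0.0948 at p = 0.20 and 0.9033 at p = 0.40. The probability of stopping early at p = 0.20 is 0.549, and the expected size is 17 + (1 − 0.549) × 20 = 26.0. The stated design is reproduced. The documents state no error rate or power for the biomarker tests.

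**2. Assumptions.** The documents give neither marker positivity by cohort nor 12-week PFS by cohort, so both are varied. The 40% v 20% scenario borrows P1 and P0 as a plausible spread; the protocol applies the same pair to both cohorts. Sidedness of the 5% level is not stated, and two-sided is assumed. The marker has no effect inside either cohort.

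**3. Expected pooled contrast.** With equal cohorts, success of 40% v 20% and positivity of 90/10:

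- marker-positive: 0.9 × 0.40 + 0.1 × 0.20 = 0.38
- marker-negative: 0.1 × 0.40 + 0.9 × 0.20 = 0.22

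The 16-point gap comes entirely from histology.

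**4. Binary outcome.** Simulated rejection rates at 5%, pooled Pearson chi-square against Mantel-Haenszel stratified by cohort. Repeat runs of 6,000 to 20,000 trials agree to within about one percentage point.

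| Success, cohort A v B | Positivity, A/B | Pooled, 37+37 | Pooled, 3/17 rule applied | Stratified, 37+37 |
|---|---|---|---|---|
| 40% v 20% | 95/5 | 40% | 33% | 4% |
| 40% v 20% | 90/10 | 34% | 26% | 5% |
| 40% v 20% | 80/20 | 20% | 16% | 5% |
| 40% v 30% | 95/5 | 12% | not tabulated | 4% |
| equal (30%) | 80/20 to 95/5 | 5% | not tabulated | 4-5% |

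The stopping rule matters because a cohort with true success of 20% stops at 17 with probability 0.549. Section 10.4 lets accrual continue during the interim analysis, so the true figure may lie between the two pooled columns.

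**5. Log-rank, the test named for PFS and OS.** Exponential PFS, censoring at 52 weeks, 37+37 patients, 5,000 runs. For 40% v 20% the cohort hazard ratio is ln(0.20)/ln(0.40) = 1.76.

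| 12-week PFS | Positivity | Unstratified | Stratified |
|---|---|---|---|
| 40% v 20% | 70/30 | 15.6% | 5.5% |
| 40% v 20% | 90/10 | 46.1% | 5.0% |
| 40% v 20% | 95/5 | 55.6% | 5.9% |
| 40% v 30% | 70/30 to 95/5 | 8.2-18.4% | 5.0-7.1% |
| equal (40%) | 70/30 to 95/5 | 5.4-6.0% | 4.9-6.0% |

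With one cohort held at 17 patients (40% v 20%, 90/10), the rates are about 30% unstratified and 6% stratified. As a ceiling, take a marker identical to cohort. Events are 74 × [1 − (0.40^(52/12) + 0.20^(52/12))/2] ≈ 73, and the Schoenfeld formula Φ(ln 1.76 × √73 / 2 − 1.96) gives about 67%.

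**6. Price of stratifying.** At 95/5 positivity, 0.05 × 37 = 1.85, so about two patients per cohort are discordant with their cohort. Power of the stratified test for a within-cohort odds ratio of 4 (37+37, about 30% success) is then about 16%, against about 76% at 50/50 positivity.

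**The case against.** The strongest reply is that pooling is never stated. Section 5.1 says without restriction that analysis is by stratum. The count of 74 can be read as a collection target, and the combined-series threshold concerns serum slopes, which nothing in the documents ties to histology. This stands in part: a reader might infer that the plan prescribes pooled tests, and the text does not go that far. But section 5.1's sentence closes the description of the two-stage rule, and section 13 does not carry it over. Nor does the SAP treat it as a blanket rule. Its Appendix I relates the growth modulation index to response, PFS and OS across both cohorts, and then labels separate analyses by cohort.

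Two further readings go beyond the documents. One is that MDM2 defines a cohort. Section 4.1 says characterised by, and refers to amplification on FISH; the test is expression by immunohistochemistry, cohorts are assigned by central pathology, and no positivity rates are given. The other is that the protocol expects the cohorts to differ. Section 10.4 uses the same P0 and P1 for both. Section 4.1 quotes 5-year survival of around 80% for ALT-WD and about 50% for high-grade myxoid/round cell disease, but these are not 12-week outcomes on pazopanib. With equal outcomes there is no material inflation.

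It is also fair that testing markers against histopathological parameters would show an MDM2-histology association. Seeing that association does not adjust the outcome tests for it.

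**Conclusion.** The point holds as a weakness of method in a secondary, translational analysis. Section 13 reads as one combined series and secures neither stratification nor adjustment by cohort, while MDM2 probably follows histology closely. If followed as it reads, it can present a histology difference as a marker effect.

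The size is conditional on assumptions the documents neither give nor exclude. At 40% v 20% success and 80/20 to 95/5 positivity, the false-positive rate of a pooled 5% chi-square is about 20-40%, or 16-33% with the stopping rule. It is about 12% at 40% v 30% with 95/5 positivity, and about 5% when outcomes are equal. Log-rank rates are somewhat higher. The risk is greatest for MDM2; for the other markers the documents give no basis for a figure.

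The primary endpoint and the 3/17 and 11/37 rules are unaffected. Stratifying will not separate predictive from prognostic value, because there is no control arm.

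**What to change.** In section 13:

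- State that every marker-outcome test is stratified by cohort: Mantel-Haenszel for 12-week PFS (which currently has no named test) and for response, stratified log-rank for PFS and OS, and Cox with cohort as the stratum. Show within-cohort estimates beside each result.
- Report MDM2 within cohort only.
- Reconcile the stepwise Cox model with the sentence ruling out multivariate analysis, so that it is clear whether any adjusted model will be fitted.

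This needs a few sentences and stratified options in the same programs, and no new data. The statistical cost is real: for markers that nearly coincide with histology, above all MDM2, the stratified analysis will have little power. The report should say so, and should not read a null MDM2 result as evidence of no effect.

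### Stepwise Cox selection over about 107 tissue markers in at most 74 patients would almost certainly select null markers, and the plan does not make clear whether multivariable analysis of biomarkers is intended

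*Protocol*

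**What the plan says.** All of this is in protocol section 13, under the study of biomarkers.

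- **Survival analysis.** The effect of histological, immunohistochemical and molecular factors on PFS and OS is to be examined by log-rank test and then by a "Cox proportional hazards model using stepwise selection to identify the independent predictors of poor outcome".
- **Next paragraph.** "We do not plan to use multivariate analysis to analyse biomarkers"; univariate pre-post tests are to take its place.
- **Tissue panel.** An "RT-PCR low density expression array containing 94 angiogenesis-related genes will be analysed"; at least 12 antibodies; microvessel density; and PIK3CA mutation status. Further tests may be added.
- **Serum panel.** "The Luminex technology will be employed for the analysis of 12 cytokines", measured serially. The serum kinetics have their own paragraph, which follows the no-multivariate statement and uses slopes and the Wilcoxon signed-rank test.
- **Error control.** A 5% significance level is stated next to the chi-square tests. Nothing is said about multiplicity, stepwise entry or removal, the number of candidates, or validation.

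Protocol 5.1 says that the statistical analysis is done in each stratum, and 10.4 says the same of the Kaplan-Meier estimates. Section 13 does not say whether this carries over to the biomarkers. SAP 1.16.3 repeats the translational objectives, but the SAP text available contains no biomarker analysis.

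**The concern.** Stepwise selection of independent predictors is a multivariable analysis. An analyst who takes both paragraphs at face value cannot comply with both, and whichever is chosen after the data are seen becomes a post hoc choice.

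The larger problem is the model itself. When candidates outnumber patients, a stepwise procedure finds apparent predictors even if no marker matters. The markers it keeps are those with the most extreme estimates, so their hazard ratios are overstated, and the p-values printed for the final model take no account of the search. Protocol 12.6.2 plans separate publication of the translational results, so such markers could reach print as independent predictors.

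There is also an unanswered design question. Protocol 4.1 describes the subtypes as biologically different and characterises the well-differentiated/dedifferentiated group by 12q13-21 amplification, which includes MDM2. MDM2 is one of the antibodies. If the cohorts were pooled without stratification, a marker like this could stand in for histology.

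**Working it through.** **1. The cap on the data.** Protocol 10.4 gives a Simon optimal design with P0 = 20%, P1 = 40%, 17 then 37 patients per stratum, stopping at 3 or fewer successes and requiring 11 or more of 37. The exact binomial calculation gives a type I error of 0.0948 and power of 0.9033, and a search returns the same design as optimal. The plan's figure reproduces: 2 × 37 = 74 patients at most, or 2 × 17 = 34 if both cohorts stopped at stage one with no further accrual.

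**2. Candidates for the Cox model.**
- Genes: the listed groups give 28 + 37 + 10 + 13 + 5 = 93 (the text says 94; with the 2 controls the list has 95).
- Tissue candidates: 93 genes + 12 antibodies + 1 microvessel density + 1 PIK3CA = 107.
- With the 12 cytokines, which the Cox sentence does not name: 107 + 12 = 119.

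The antibody list is a minimum and additions are allowed, so these are lower bounds.

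**3. Events per candidate.** The documents give no event count. Assuming 63 events (85% of 74), with a range of 44 (60%) to 74, the ratio for 107 candidates is 63/107 = 0.59, with a range of 44/107 = 0.41 to 74/107 = 0.69.

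**4. Separate tests at 5%, all markers null and independent.**
- Expected false positives per endpoint: 107 × 0.05 = 5.35.
- P(at least one) = 1 − 0.95^107 = 99.6%.
- For PFS and OS together: 2 × 107 = 214 tests, 214 × 0.05 = 10.7 expected.

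**5. Stepwise Cox under the global null.** The simulation used 200 replicates per row and binary markers with prevalence 25% to 75%. Entry was by score test at p < 0.05, removal at p > 0.10, and the model was capped at 12 terms. These settings are assumptions, because the protocol states none. The larger panel was run with 118 markers, one fewer than the 119 counted above.

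| Patients | Candidates | Event rate | Correlation | At least 1 selected | Mean selected | 5 or more |
|---|---|---|---|---|---|---|
| 74 | 107 | 85% | 0.3 | 98.5% | 8.5 | 82.5% |
| 74 | 118 | 85% | 0 | 100% | 10.1 | 93.5% |
| 74 | 118 | 85% | 0.3 | 98.5% | 9.0 | 85.0% |
| 74 | 118 | 60% | 0.3 | 99.5% | 9.2 | 84.0% |
| 37 | 118 | 85% | 0.3 | 100% | 8.7 | 91.0% |
| 74 | 13 | 85% | 0.3 | 45.0% | 0.65 | 0% |
| 74 | 12 | 85% | 0 | 48.0% | 0.69 | 0% |

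The first marker enters on its univariable test, so the chance of at least one selection is the same as for univariable testing. What stepwise adds is further null terms (with 107 candidates, a mean of 8.5 selected against 5.8 univariably significant in the same simulated data) and the label of independence.

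**6. Overstatement.** For a marker with 50% prevalence, two-sided p < 0.05 needs |log HR| above about 1.96 × 2/√events. With 63 events this is 3.92/7.94 = 0.494, or HR 1.64. With 44 events it is 3.92/6.63 = 0.591, or HR 1.81; with 74 events, 3.92/8.60 = 0.456, or HR 1.58. A null marker entering first, whose true HR is 1, would therefore be reported at about 1.6 to 1.8 or more (or the reciprocal).

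**7. What multiplicity control would cost.** Bonferroni gives a lower bound on power, since false-discovery-rate control by Benjamini-Hochberg rejects everything that Bonferroni does. The level is 0.05/107 = 0.00047. By the Schoenfeld formula with 50% prevalence and 63 events, power is 23% for HR 2 (12% to 30% over 44 to 74 events) and 80% for HR 3 (56% to 89%). At an uncorrected 5% and 63 events it is 79% and 99%.

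**The case against.** The strongest reply is that the two paragraphs can be reconciled. Pre-post tests cannot replace a survival model. They suit serial serum measurements, which the following paragraph takes up, and the Cox sentence names tissue factors and not serum. On that reading, Cox is for tissue and paired univariate tests are for serum. This is a fair reading. A reader might infer a flat contradiction, but the documents support only an ambiguity: the sentence says biomarkers without limit, under a heading that covers both tissue and serum. Resolving it in the plan's favour leaves the stepwise model in place, so the main problem stands.

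A reader might also infer that the histologies are pooled with no adjustment. Section 13 does not say so. Protocol 5.1 points to analysis per stratum, and histological factors are among those named for the survival analysis. Confounding by histology is therefore conditional on pooling. If analysis is per stratum it falls away, but at most 37 patients are left per model.

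A third tempting reading is that the near-100% false-positive figure condemns stepwise selection alone. It does not. It is the family-wise error of separate 5% tests and applies equally to an uncorrected univariable analysis.

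Finally, this is a translational sub-study. It does not touch the Simon decision rule, and that limits the severity.

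**Conclusion.** The point holds. As written, the stepwise Cox model has about 107 candidates (about 119 if the cytokines are included) for at most 74 patients, with well under one event per candidate. If no marker had any effect, it would still select at least one in 98.5% to 100% of trials and typically eight to ten. Results called independent predictors would not be credible.

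The percentages depend on the assumed 5% entry level, event rates, marker prevalence and correlation. The simulated conclusion barely moved across the event rates, correlations and large panels tried. It changed only when the list was cut to 12 or 13 markers, where the chance of a null selection was 45% to 48%.

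Whether multivariable analysis is intended for all biomarkers, and whether the cohorts are to be analysed separately, are open questions in the text and should be settled before the data are analysed. The change should be made, but the primary analysis is not at risk.

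**What to change.** In protocol section 13, and in a biomarker section of the SAP:

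1. Delete the stepwise Cox model and the claim of independent predictors. This agrees with the plan's own no-multivariate sentence and removes the ambiguity.
2. Report a univariable Cox hazard ratio with 95% CI for every marker, for PFS and OS, stratified by cohort.
3. Control the false discovery rate across the panel. Otherwise label all results exploratory and state the number of tests (at least 214 for PFS and OS on the tissue panel). Without this step the univariable analysis has the same false-positive problem.

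The cost is a wording change with no new data. The sponsor gives up any claim of independent predictors, and fewer markers will be declared significant. Under Bonferroni, the strictest case, power with 63 events would be about 23% for HR 2 and 80% for HR 3; false-discovery-rate control would do no worse.
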